1 INTRODUCTION

1.1 BACKGROUND

The aim of oxygen therapy is to deliver sufficient oxygen to tissues to maintain tissue function and avoid adverse consequences, whilst minimising oxidative stress and oxygen toxicity. It is unclear how best to achieve this balance in premature infants, who are at high risk of developing oxygen-related morbidities because of their relative lack of antioxidant protection.

Oxygenation can be monitored by measurement of pulse oximeter oxygen saturation (SpO_2), which estimates the percentage of haemoglobin (an oxygen carrying molecule in red blood cells) binding sites occupied by oxygen, using a transcutaneous monitor to measure transcutaneous partial pressure of oxygen (TcPO_2) which is the amount of oxygen diffusing across the skin, or by measuring the partial pressure of oxygen (PaO_2) dissolved in arterial blood.

The gold-standard for assessing oxygen levels is accepted to be arterial oxygen tension (PaO_2) but measuring this is invasive and it cannot be measured continuously. SpO_2 monitoring provides a continuous, non-invasive measure, but SpO_2 and PaO_2 are related in a complicated, non-linear way. TcPO_2 and PaO_2 levels correlate well and are related in a linear way.

In the early 2000s a number of cohort studies gave conflicting results about the optimum oxygen range in preterm babies. Therefore consensus was achieved to conduct a prospective meta-analysis of oxygen targeting studies, of sufficient power to test the hypothesis that a strategy of maintaining a functional SpO_2 level in a “lower” (85-89%) versus a “higher” (91-95%) range early in the course of extremely low gestational age neonates reduces the incidence of severe ROP without increasing important adverse neonatal outcomes⁽¹⁾. The Neonatal Oxygenation Prospective Meta-analysis (NeOProM) involved data from the SUPPORT, BOOST II Australia, BOOST NZ, COT, and BOOST II UK trials and was powered to detect a small but important 4% increase in death or severe disability in survivors⁽²⁾.

Three recent systematic reviews and meta-analyses using data from the five studies that make up the NeOProM collaboration have all revealed a significant increase in the risk of death associated with targeting infants to the lower SpO_2 range. Saugstad OD, Aune D⁽³⁾ found relative risks (RR; 95% CIs) comparing a low versus a high oxygen saturation target were 1.41 (1.14-1.74) for mortality at discharge or at follow-up. Manja and Lakshminrusimha⁽⁴⁾ found a significant increase in mortality before hospital discharge in infants targeted to the lower SpO_2 range (RR, 1.18 [95% CI, 1.03-1.36]). Askie et al.⁽⁵⁾ found a lower SpO_2 target range significantly increased the incidence of death at 18 to 24 months corrected age (typical RR 1.16, 95% CI 1.03 to 1.31; typical RD 0.03, 95% CI 0.01 to 0.05; 5 trials, 4873 infants).

As described above, the search for the optimum oxygen level to target preterm infants is still ongoing. Although there is very good evidence targeting infants to a lower oxygen level results in harm, it is not clear whether the higher target level used in the NeOProM studies achieves the optimum survival advantage.

1.2 RATIONALE FOR STUDY

There is still considerable uncertainty about what oxygen levels premature babies should be targeted to. Although there is clear evidence that targeting babies to a lower oxygen saturation (SpO_2) level is associated with harm, it is not clear whether we have found the optimum oxygen target level which maximises survival benefit.

We believe the question of oxygen targeting is an important one in neonatology, and this proposal would be a safe and reliable way of characterising the actual oxygen levels achieved at a higher SpO_2 target range. We hope the results of this study would inform a larger research study using higher SpO_2 limits and powered to analyse clinical outcomes.

Because very high oxygen levels may cause harm (such as increasing the risk of retinopathy of prematurity - a condition that although treatable can affect vision), it is prudent to increase oxygen target limits by small increments, and for a short amount of time. This is why we are proposing a small increase in SpO₂ target limits from 90-95% to 92-97%, for a short period (6 hours).

Based on previous research it is very unlikely that these slightly higher ranges will be associated with hyperoxia (high levels of oxygen in the blood), but it is also sensible to monitor oxygen levels by more than just SpO₂, as SpO₂ is not the best way of measuring hyperoxia. This is why we are proposing to use transcutaneous oxygen monitoring (TcPO₂) throughout the study, as previous research has demonstrated TcPO₂ is better at detecting hyperoxia than SpO₂.

In order to minimise confounding factors, we propose that infants act as their own controls, being randomised either a higher or standard SpO₂ target limit, and then crossing over to the other SpO₂ target range after 6 hours.

As described above, we feel that the research question is an important one, and our proposal will be able to answer it. We believe this proposal minimises risk to infants. Although previous research has suggested a very high levels of oxygen are associated with increased risk of ROP, there is good evidence to suggest that our proposed slightly higher SpO₂ range will not be associated with hyperoxia, and the use of TcPO₂ is an additional safety measure. We need to balance the risk of ROP with the very real risk that we are missing the opportunity to reduce mortality in premature babies by not using an SpO₂ target range that is high enough to achieve maximum survival advantage.

Written informed consent will be sought from the parents of eligible infants by research staff trained in GCP, and all information will be handled in accordance with Caldicott principles.

2 STUDY OBJECTIVES

2.1 OBJECTIVES

2.1.1 Primary Objective

To discover the percentage time spent above an SpO₂ of 97% and below an SpO₂ of 90% when infants are targeted to an SpO₂ range of 92-97% compared to 90-95%

2.1.2 Secondary Objectives

To discover the percentage time spent above a TcPO₂ of 80mmHg and below a TcPO₂ of 50mmHg when infants are targeted to an SpO₂ range of 92-97% compared to 90-95%

To discover the variability in SpO₂ (measured by standard deviation) when infants are targeted to an SpO₂ range of 92-97% compared to 90-95%

To discover the variability in TcPO₂ (measured by standard deviation) when infants are targeted to an SpO₂ range of 92-97% compared to 90-95%

In infants who are undergoing PaO₂ measurement as part of their routine care describe the PO₂ values observed in the two target ranges.

To generate a pooled frequency histogram of percentage time at each SpO₂ point between 80 and 100% for infants targeted to an SpO₂ range of 92-97% compared to 90-95%

To generate a pooled frequency histogram of percentage time at a TcPO₂ of below 30mmHg, 30-39.9mmHg, 40-49.9mmHg, 50-59.9mmHg, 60-69.9mmHg, 70-79.9mmHg, and 80mmHg and above for infants targeted to an SpO₂ range of 92-97% compared to 90-95%

3 STUDY DESIGN

Summary

This study is a single centre randomised crossover study. Infants born at less than 29 weeks gestation, greater than 48 hours of age and receiving supplementary oxygen would be eligible for inclusion. The study is at the Royal Infirmary of Edinburgh. Total study time is 12 hours for each infant (6 hours at the standard 90-95% range used in our unit, and 6 hours at 92-97%). It is a crossover study with infants acting as their own controls.

A complete list of all monitoring that will be carried out is shown below:

1. SpO₂ monitoring
2. TcPO₂ monitoring
3. Heart rate monitoring (used to validate SpO₂ readings as described below)
4. Arterial gas sampling (only if conducted by the direct care team as part of the routine care of the infant will these be recorded. No extra blood samples will be taken as part of the study)

[figure not shown]
Design

Each infant will be monitored simultaneously with an SpO₂ monitor and TcPo₂ monitor, with data recording starting from the time the transcutaneous monitor finishes calibrating. SpO₂ readings will be downloaded directly from the multiparameter patient monitor. SpO₂ will be measured using a Siemens Infinity SC7000 multiparameter monitor (Siemens Medical Systems, Danvers MA). This monitor uses Siemens' Oxisure pulse oximetry technology and Nellcor Oximax (Nellcor Puritan Bennett, CA, USA) saturation probes and incorporates ECG to reduce motion artefact. To reduce the influence of artefact further, data from an infants chest leads (recording heart rate) will also be downloaded. If there is a greater than 10 beats per minute difference between heart rate measured from the pulse oximeter and heart rate measured from the chest leads, SpO₂ for that time point will be disregarded.

TcPO₂ will be measured using a SenTec Digital Monitoring System with OxiVent sensor (SenTec AG, Switzerland, European patent No. 1535055, CE 0120). TcPO₂ is calculated by dynamic fluorescence quenching which measures oxygen molecules present in the vicinity of a fluorescent dye incorporated within the sensor surface. The sensor is operated at a constant temperature of 43 degrees Celsius. Control of sensor temperature and application duration are designed to meet all applicable standards and this monitoring device is used routinely in many neonatal units, with transcutaneous monitoring part of the monitoring equipment we use in selected infants in our unit and being transported by our local neonatal transport team. Temperature is supervised by two independent circuits, as well as by the monitor firmware.

Transcutaneous data will be transferred contemporaneously to a bedside PC via the proprietary software V-STATS (with V-CareNeT) version 4.01 (SenTec AG, [name]). We will ensure the time on the monitor is synchronised with the time displayed on the electronic patient record system recording SpO₂ and heart rate. V-STATS software can identify any spurious spikes in TcPO₂ caused by air bubbles and these identified segments of data will be discarded. Artefact has not significantly affected readings during the routine use of this monitor previously on our neonatal unit and with our neonatal transport team. The site of the transcutaneous probe will be rotated on each infant every 2 hours.

SpO₂, TcPO₂ and heart rate data will be recorded every second. The time of any arterial oxygen samples taken routinely during the study will be recorded from the unit blood gas analyser (ABL800 FLEX, Radiometer, Denmark, 2005).

4 STUDY POPULATION

4.1 NUMBER OF PARTICIPANTS

A sample of 20 preterm babies born at the Royal Infirmary of Edinburgh meeting the inclusion criteria will be recruited. Because we are obtaining pilot data to inform the design of future studies we do not have a basis for a power calculation

4.2 INCLUSION CRITERIA

Infants born at less than 29 weeks gestation

Infants greater than 48 hours of age

Infants who are receiving supplementary oxygen

4.3 EXCLUSION CRITERIA

Congenital anomalies that would affect oxygenation (eg. cardiac defects, congenital diaphragmatic hernia)

4.4 CO-ENROLMENT

The neonatal unit frequently conducts research projects - both single centre and multicentre projects. There is no contraindication to participating in this research if currently enrolled in another study. We have found that parents greatly appreciate being involved in studies, and are unlikely to be overwhelmed by being approached for multiple studies. Parents are made aware that they are free to decline to participate in any study without giving a reason.

5 PARTICIPANT SELECTION AND ENROLMENT

5.1 IDENTIFYING PARTICIPANTS

Potential participants would initially be identified by the direct care team.

5.2 CONSENTING PARTICIPANTS

The parents of babies born at less than 29 weeks gestation will be approached by a member of the research team and given an information leaflet. If parents then would like to discuss the study further, a member of the research team (with appropriate GCP training) will discuss this with them at their convenience, and ask for consent if they are willing to participate.

5.2.1 Withdrawal of Study Participants

Parents will be free to withdraw their infant from study at any time without having to give a reason. As the study involves routinely used equipment and is of short duration it is not anticipated that this will happen.

6 STUDY ASSESSMENTS

6.1 STUDY ASSESSMENTS

By targeting babies to higher oxygen saturation levels there is a possibility that they will be subjected to higher oxygen levels than previously recommended for short periods. Previous research and audit of our unit's blood gas machine results suggests that at a SpO₂ target range of 92 to 97% this is very unlikely, and is in fact more likely to keep babies' within the previously suggested oxygen tension target range. In addition, the use of the transcutaneous monitor with upper limit alarms enabled, mitigates the risk of high PaO₂ levels, and the very short study period means infants are only targeted to slightly higher oxygen levels for 6 hours.

Transcutaneous oxygen monitoring is part of routine clinical practice. The use of transcutaneous probes have in the past been associated with transient skin redness in preterm babies' skin (as the probe is heated). Modern devices use a lower temperature than those used in previous research, and probes have safety mechanisms whereby the probe is no longer heated if it is left in place for longer than the recommended time.

7 DATA COLLECTION

The study diagram is section 3 details the timepoints and data collected during each study period. Collection of data is contemporaneous and checked for validity as described above. Valid and anonymised SpO₂ and TcPO₂ will then be used in the analysis.

8 STATISTICS AND DATA ANALYSIS

8.1 SAMPLE SIZE CALCULATION

This is a pilot study to inform a larger study of SpO₂ and possibly TcO₂ ranges.

Recruitment is planned to end when 20 babies have been recruited and randomised. Based on the frequency of delivery of preterm babies in our unit we estimate the study to last 1 year.

8.2 PROPOSED ANALYSES

For each group we will calculate the percentage of readings above an SpO₂ of 97% and below an SpO₂ of 92%. These percentages will then be compared between groups by using a Student's T-test.

The variability of SpO₂ for each group will be expressed by calculating the standard deviation of all the valid SpO₂ data points in each group. Comparison between variability between groups will be performed by Student's T-test.

Pooled SpO₂ data from each infant randomised to the 90-95% SpO₂ group will then be used to generate time at each SpO₂ point for the group as a whole, expressed as a percentage of the total number of valid SpO₂ readings. This process will then be repeated for the 92-97% SpO₂ target range group.

Pooled TcPO₂ data from each infant randomised to the 90-95% SpO₂ group will then be used to generate time within the following TcPO₂ ranges for the group as a whole: below 30mmHg, 30-39.9mmHg, 40-49.9mmHg, 50-59.9mmHg, 60-69.9mmHg, 70-79.9mmHg, and 80mmHg and above. This will be expressed as a percentage of the total number of valid TcPO₂ readings. This process will then be repeated for the 92-97% SpO₂ target range group.

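### The primary objective measures time below SpO₂ 90%, but Section 8.2 analyses time below 92%, which scores readings of 90 and 91% as low even though they are on target in the 90-95% period

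*Combined protocol and SAP*

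**What the plan says.** Section 2.1.1 gives the primary objective as "To discover the percentage time spent above an SpO₂ of 97% and below an SpO₂ of 90" per cent, comparing the 92-97% target with the 90-95% target.

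Section 8.2 opens with the only calculation that corresponds to this objective: "the percentage of readings above an SpO₂ of 97% and below an SpO₂ of 92" per cent. It then gives the test: "These percentages will then be compared between groups by using a Student's T-test". It states no significance level or sidedness, and it does not call this analysis primary.

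Section 3 describes each infant's exposure as "6 hours at the standard 90-95% range used in our unit, and 6 hours at 92-97" per cent, and adds: "It is a crossover study with infants acting as their own controls". The comparator is therefore the 90-95% period in the same infants, not a separate group.

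One other planned output bears on the point. Section 2.1.2 lists among the secondary objectives: "To generate a pooled frequency histogram of percentage time at each SpO₂ point between 80 and 100" per cent, for each target. Section 8.2 describes how the readings are pooled for it but specifies no comparison between targets.

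**The concern.** Time below 90% and time below 92% are different outcomes. The only section that turns the primary objective into a calculation uses a cut-off that the objective does not.

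The substitution is also not neutral. The objective's pair, 90 and 97, marks the outer limits of the two target ranges taken together, so no on-target reading in either period is counted as out of bounds. The Section 8.2 pair, 92 and 97, is the higher target range itself. An infant held exactly as intended in the 90-95% period can still accumulate low readings under 8.2. An infant held exactly as intended in the 92-97% period cannot.

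Two things are at stake. First, Sections 1.2 and 8.1 say the study is to inform a larger one. If the 8.2 result is reported as the primary finding, part of the apparent reduction in low saturation will be standard-period readings that were on target. Second, with two lower cut-offs on file and no order of precedence, the choice between them could be made after the data are seen.

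**Working it through.** The plan gives no expected value, SD, effect size or power for this outcome, so there is no figure of its own to reproduce. The check has three steps.

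**1. The two definitions side by side**

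| | Upper cut-off | Lower cut-off |
|---|---|---|
| Section 2.1.1, primary objective | above 97% | below 90% |
| Section 8.2, analysis | above 97% | below 92% |
| Standard target (Sections 1.2 and 3) | 95% | 90% |
| Higher target (Sections 1.2 and 3) | 97% | 92% |

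The 8.2 lower cut-off equals the lower limit of the higher target. It lies 92 − 90 = 2 points above the lower limit of the standard target.

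**2. On-target values scored as low (no distribution needed)**

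| Target | Whole-number values | Below 90% | Below 92% |
|---|---|---|---|
| 90-95% | 90, 91, 92, 93, 94, 95 | 0 of 6 | 2 of 6 (90 and 91) |
| 92-97% | 92, 93, 94, 95, 96, 97 | 0 of 6 | 0 of 6 |

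An infant always on target and spread evenly over 90-95% would score 0% low under Section 2.1.1 and 2/6 = 33% low under Section 8.2. Perfect, even compliance is a limiting case, not a forecast.

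**3. Illustration of size**

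Assumptions, none of them in the documents: readings are normal before rounding to whole numbers; they are centred on each range's midpoint, (90 + 95)/2 = 92.5 and (92 + 97)/2 = 94.5; the SD is the same in both periods and lies between 2 and 5. A rounded reading below k means an unrounded value below k − 0.5, so

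P(below k) = Φ((k − 0.5 − mean)/SD).

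For SD 2 in the standard period: below 90% is Φ((89.5 − 92.5)/2) = Φ(−1.5) = 6.7%, and below 92% is Φ((91.5 − 92.5)/2) = Φ(−0.5) = 30.9%. In the higher period: Φ((89.5 − 94.5)/2) = Φ(−2.5) = 0.6%, and Φ((91.5 − 94.5)/2) = Φ(−1.5) = 6.7%.

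Percentage of readings scored low (standard, higher, then the difference in points, taken before rounding):

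| SD | Below 90% | Below 92% | Ratio of differences |
|---|---|---|---|
| 2 | 6.7, 0.6, **6.1** | 30.9, 6.7, **24.2** | 24.2/6.1 = 4.0 |
| 3 | 15.9, 4.8, **11.1** | 36.9, 15.9, **21.1** | 21.1/11.1 = 1.9 |
| 4 | 22.7, 10.6, **12.1** | 40.1, 22.7, **17.5** | 17.5/12.1 = 1.4 |
| 5 | 27.4, 15.9, **11.6** | 42.1, 27.4, **14.6** | 14.6/11.6 = 1.3 |

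Readings of exactly 90 or 91% in the standard period make up Φ((91.5 − 92.5)/SD) − Φ((89.5 − 92.5)/SD) of all readings: 24.2, 21.1, 17.5 and 14.6% for SD 2, 3, 4 and 5. As a share of all standard-period readings below 92%, that is 78, 57, 44 and 35%. In this model the two ranges differ by a 2-point shift, and the cut-offs also differ by 2 points. The whole difference at the 92% cut-off is therefore numerically equal to the standard-period readings at 90-91%, all of them on target.

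**The case against.** The strongest reply is that the information is not lost. Section 8.2 also produces the distribution of pooled readings over SpO₂ points for each target, as percentages of all valid readings, so pooled time below 90% is 100 minus the sum from 90 to 100. That is correct, and it means a descriptive answer to the objective can be recovered. The histogram still gives no per-infant summary and no test at 90%, so it does not supply the comparison between targets that Section 8.2 sets out.

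A second reply is that any shared cut-off reflects the shift between targets. On the low side alone, 90% is the lower limit of the standard range, and readings of 90-91% in the higher period are off target yet not counted as low. The illustration itself shows 6.1 to 12.1 points in favour of the higher target at 90%. This stands. The even treatment belongs to the 90/97 pair, and time below 92% is a different outcome rather than a biased estimate of the same one. It misleads when it is presented as the primary objective's result or as time below target.

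Third, this is a 20-infant pilot, for which Section 4.1 says: "Because we are obtaining pilot data to inform the design of future studies we do not have a basis for a power calculation". Readings are stored every second, so either cut-off can be computed later, and the part of the objective above 97% is unaffected. All true. But a pilot's value lies in clearly defined estimates, and the fact that both can be computed is what leaves the choice open after the data are seen.

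Finally, the documents do not say which section holds the slip. Giving precedence to the stated primary objective is the natural default. If 92% was intended, Section 2.1.1 is wrong, and the plan would have to justify a cut-off inside the standard range.

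**Conclusion.** The concern holds. The low-side primary outcome has two incompatible definitions in current text, and the one attached to the analysis counts 2 of the 6 on-target values of the standard range as low and none of the higher range's. Followed as written, Section 8.2 tests an outcome other than the stated primary one, in a direction that enlarges the apparent advantage of the higher target.

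These conclusions rest on the documents alone. The amount does not: a ratio of about 1.3 to 4 holds for rounded-normal readings centred on the range midpoints with equal SDs of 2 to 5. Other distributions would give other figures. The point must be settled before analysis because it concerns the definition of the primary outcome.

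**What to change.** In the first paragraph of Section 8.2, change the lower cut-off from 92% to 90% so that it matches Section 2.1.1, and state that this is the analysis of the primary objective. If time below 92% is of interest, list it separately as descriptive only, with a note that 90-91% is within the standard target.

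The cost is one number and a sentence or two, made as an amendment before the data are analysed. No new data are needed, and neither the target ranges nor bedside practice changes.

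If the team did intend 92%, Section 2.1.1 has to be amended instead, with the reason for the cut-off given, also before analysis. In either case one lower cut-off should remain on file for the primary comparison.

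### Section 8.2 does not carry the crossover into the analysis: pairing and unit of analysis are unstated, SpO₂ variability is one SD per range, and there is no period term

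*Combined protocol and SAP*

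**What the plan says.** Section 1.2 gives the reason for the design: "In order to minimise confounding factors, we propose that infants act as their own controls". Section 3 repeats it: "It is a crossover study with infants acting as their own controls". Each infant spends 6 hours at each target range, in randomised order, and "SpO₂, TcPO₂ and heart rate data will be recorded every second".

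Section 8.2 is the only analysis text. It calculates, for each group, the percentage of readings above and below the SpO₂ thresholds, and continues: "These percentages will then be compared between groups by using a" Student's t-test. Variability is obtained by "calculating the standard deviation of all the valid SpO₂ data points in each group", and this too is compared by Student's t-test. The histogram paragraph refers to "Pooled SpO₂ data from each infant randomised to the 90-95% SpO₂ group", although in a crossover every infant receives both ranges. Pairing, a per-infant summary, period and sequence are not mentioned.

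For TcPO₂, section 2.1.2 sets two comparative objectives: "To discover the percentage time spent above a TcPO₂ of 80mmHg and below a TcPO₂ of 50mmHg" and "To discover the variability in TcPO₂ (measured by standard deviation"), each under one range compared with the other. Section 8.2 gives only pooled TcPO₂ bins per range.

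**The concern.** The crossover was chosen so that differences between infants drop out of the comparison. They drop out only if the analysis works on within-infant differences, and section 8.2 does not say that it will. Its wording leaves three analyses open:

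- a paired test on infant values, which is sound apart from period;
- an unpaired test on 20 + 20 infant values, which is conservative and loses the precision the design was meant to buy;
- a test on individual readings, which is strongly anti-conservative.

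The variability comparison is a different matter. It is defined explicitly, and the definition does not work. The study is also meant to inform a larger trial. The quantity such a trial needs for its sample size is the SD of the within-infant differences, and group-level figures cannot supply it.

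**Working it through.** **Inputs from the documents.** 20 infants (4.1, 8.1); two 6-hour periods and randomised order (1.2, 3); one reading per second (3). That gives 6 × 3,600 = 21,600 readings per infant-period at most, and 20 × 21,600 = 432,000 per range. The documents state no alpha, power, effect size, SD or correlation, so there is no planned figure to reproduce.

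**Assumptions.** Two-sided 5% level; equal SDs in the two ranges; normal data; within-infant correlation ρ of 0.3, 0.5 or 0.7; intraclass correlation of readings (ICC) of 0.01 to 0.10. The results show direction and range only.

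**1. Variability as defined.** One SD over all readings in a range gives one value against one value, so a t-test has no replication. The pooled SD also mixes two sources: pooled SD = √(within² + between²). With an assumed within-infant SD of 4 points and a between-infant SD of 1, 2 or 3, it is 4.12, 4.47 or 5.00, though the within-infant variability is 4 throughout.

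**2. Unpaired test on infant values.** Paired SE = SD·√(2(1−ρ)/20); unpaired SE = SD·√(2/20); ratio = 1/√(1−ρ). Type I error and power are simulated with 20 pairs. In the fourth column the effect is 0.660 SD of the differences, which gives the paired test 80% power. In the last column it is 0.5 SD of the infant values.

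| ρ | SE ratio | Unpaired type I error | Unpaired power (paired 80%) | Power at fixed 0.5 SD, unpaired / paired |
|---|---|---|---|---|
| 0.3 | 1.20 | 2.1% | 70% | 31% / 43% |
| 0.5 | 1.41 | 0.7% | 54% | 29% / 56% |
| 0.7 | 1.83 | 0.1% | 27% | 24% / 78% |

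The last two columns describe the same loss. With the absolute effect fixed, unpaired power is nearly flat, and what is forgone is the paired test's gain.

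**3. Test on readings.** The SE is understated, relative to the correct paired SE, by k = √[(1 + 21,599·ICC)(1−ρ)]. For ICC 0.05 and ρ 0.5, k = √(1,080.95 × 0.5) = 23.2. Type I error = 2(1 − Φ(1.96/k)).

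| ICC | k at ρ = 0.3 / 0.5 / 0.7 | Type I error |
|---|---|---|
| 0.01 | 12.3 / 10.4 / 8.1 | 87% / 85% / 81% |
| 0.05 | 27.5 / 23.2 / 18.0 | 94% / 93% / 91% |
| 0.10 | 38.9 / 32.9 / 25.5 | 96% / 95% / 94% |

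**4. Paired test without a period term.** A period shift adds +s to the differences in one sequence and −s in the other, with s in SDs of the differences. At a 10:10 split there is no bias, but the shift enters the error variance.

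| s | Power without term | Type I error without term |
|---|---|---|
| 0 | 80% | 5.0% |
| 0.25 | 78% | 4.4% |
| 0.5 | 72% | 2.9% |
| 1.0 | 49% | 0.6% |

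With the term, power stays at about 80% throughout. At a 13:7 split, the fraction of the shift left in the estimate is (13 − 7)/20 = 0.3. With s = 0.5 the bias is 0.3 × 0.5 = 0.15 SD, and type I error is about 6.5%, against 4.9% with the term. If order were set by simple randomisation, a split at least that uneven would occur with probability 26%.

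**5. TcPO₂.** The pooled bins can be added to give time at or above 80 mmHg and below 50 mmHg per range, but they give no within-infant comparison. The TcPO₂ SD objective has no analysis in 8.2.

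**The case against.** A Student's t-test may be paired, and sections 1.2 and 3 say plainly that infants are their own controls. A charitable reader would assume a paired test on one percentage per infant, since a t-test on percentages needs several of them per range. Pooling is named only in the histogram paragraphs. On that reading the readings-level figures describe an analysis nobody intends. The unpaired test errs on the safe side, the period effect is hypothetical, and this is a 20-infant pilot with no power target. Percentage time is also bounded and may be skewed, so simulations under normality are more precise than their inputs.

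Much of this stands. The readings-level case is the least natural interpretation and should carry least weight. The period term is the smallest part of the point, and the TcPO₂ SD gap is a mismatch between objective and analysis more than a crossover failure. The figures are illustrations.

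It does not remove the core. The phrases about groups, and about infants randomised to a range, point away from pairing. Pairing would not rescue an SD defined over all readings. Pilot status explains the absence of a power calculation, but not the absence of a unit of analysis once t-tests are planned.

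**Conclusion.** The concern holds and should be fixed. The SpO₂ variability comparison fails as written, independently of any assumption. For the percentage-time comparison the plan is silent on pairing and unit, and its wording leans towards parallel groups.

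The cost depends on how the gap is filled. A paired test leaves only the period issue: power of 72% instead of 80% for an assumed shift of 0.5 SD at 10:10. An unpaired test on infants is valid but wasteful, with an SE 1.20 to 1.83 times the paired SE. A test on readings would be badly invalid. The sizes rest on assumed ρ, ICC, period shift and normality; the directions hold across the ranges tried.

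**What to change.** Reword section 8.2 as follows.

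- For each infant and each target period, compute one percentage for each SpO₂ threshold and one SD of the valid readings.
- Compare the ranges on within-infant differences adjusted for period, by the two-period crossover t-test or a mixed model with infant random and target and period fixed. If the differences are clearly skewed, give a rank-based equivalent that respects sequence.
- Report the mean difference, its 95% CI and the SD of the differences.
- Apply the same analysis to TcPO₂ time above 80 mmHg and below 50 mmHg, and to TcPO₂ SD.
- Keep the pooled histograms as descriptive displays.

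The change is wording and a few lines of code, with no new data. The period term takes one degree of freedom (18 instead of 19). At 10:10 with no period effect, power stays at about 80%. If sequences end 13:7, the SE rises by √(400/(4 × 13 × 7)) = 1.048, or 4.8%, and power is 76% instead of 80%.

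### Section 8.2 compares one SpO₂ standard deviation per target range by a t-test, which leaves 0 degrees of freedom; neither a per-infant SD nor a paired test is stated

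*Combined protocol and SAP*

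**What the plan says.** Section 8.2 summarises SpO₂ variability by "calculating the standard deviation of all the valid SpO₂ data points in each group". The next sentence begins "Comparison between variability between groups will be performed by" and names Student's t-test, without saying whether it is paired.

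The percentage-time analysis in 8.2 is worded in the same way. It opens "For each group we will calculate the percentage of readings", above and below set limits, and again names Student's t-test. The two histogram paragraphs differ: they start from "Pooled SpO₂ data from each infant randomised to the 90-95% SpO₂ group" (then likewise for 92-97%), describe the group as a whole, and attach no test.

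The secondary objective in 2.1.2 reads "To discover the variability in SpO₂ (measured by standard deviation" and does not state a unit of analysis. On design the protocol is clear. Section 1.2 says "we propose that infants act as their own controls", and section 3 says "It is a crossover study with infants acting as their own controls". Both target ranges therefore contain the same infants, and a group in 8.2 can only mean a target range.

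**The concern.** The quantity defined in 8.2 does not support the test named for it. A t-test needs replicate values in order to estimate an error variance, and one SD per target range provides none. An analyst would have to choose the unit of analysis, and then choose between a paired and an unpaired test, possibly after seeing the data.

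Two further points follow:

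- **Lost precision.** An unpaired test would discard the within-infant comparison for which the crossover was chosen. The group language in 8.2, which refers to infants randomised to a range as in a parallel trial, makes that choice more likely.
- **A different quantity.** An SD over all readings in a range mixes fluctuation within infants with differences between infants' mean levels. The objective is better served by within-infant variability.

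The pilot is meant to inform a larger study. A later crossover would need the within-infant difference and its spread for its sample size, and a single pooled SD per range gives neither.

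**Working it through.** The plan gives no power, alpha, effect size or SD, so there is no figure of its own to reproduce.

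**Inputs from the documents.** 20 infants (4.1, 8.1); 6 hours in each range (section 3); "SpO₂, TcPO₂ and heart rate data will be recorded every second" (section 3).

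**Assumed inputs.** The within-infant correlation ρ between an infant's SDs in the two ranges is taken as 0.3, 0.5 or 0.7. A completer count of 16 is used for illustration. The SDs in step 4 are also illustrative.

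**1. Literal rule.** Each range yields one SD, from up to 20 × 6 × 3,600 = 432,000 readings. Two-sample degrees of freedom are 1 + 1 − 2 = 0, and paired degrees of freedom are 1 − 1 = 0. Run in software on one value per group, the test returns no t statistic and no p-value. This step needs no assumption.

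**2. One SD per infant per range.** A paired test has 20 − 1 = 19 degrees of freedom (critical t 2.093). With 16 complete pairs it has 15. An unpaired test on the same 20 infants would have 2 × 20 − 2 = 38 (critical t 2.024).

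**3. Cost of ignoring the pairing.** The ratio of unpaired to paired standard error is 1/√(1 − ρ). The 95% CI half-width, in units of the between-infant SD of the per-infant SDs, is t(n−1) × √(2(1 − ρ)/n) for the paired test and t(2n−2) × √(2/n) for the unpaired test. For n = 20 and ρ = 0.5, the paired half-width is 2.093 × √(1/20) = 0.468 and the unpaired one is 2.024 × √(2/20) = 0.640.

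| Assumed ρ | SE ratio | Paired, n = 20 | Unpaired, n = 20 | Paired, n = 16 | Unpaired, n = 16 |
|---|---|---|---|---|---|
| 0.3 | 1.20 | 0.55 | 0.64 | 0.63 | 0.72 |
| 0.5 | 1.41 | 0.47 | 0.64 | 0.53 | 0.72 |
| 0.7 | 1.83 | 0.36 | 0.64 | 0.41 | 0.72 |

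A simulation (200,000 runs, 20 infants, two-sided nominal 0.05) put the actual error rate of the unpaired test at about 0.021, 0.007 and 0.001 for these three correlations. At the difference a paired test detects with 80% power, the unpaired test has about 70%, 54% and 27% power.

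**4. Mixing of within- and between-infant spread.** The group-level SD is approximately √(within² + between²). Suppose the within-infant SD falls from 4.0 to 3.5, a change of −12.5%, with the same between-infant SD in both ranges. The largest between-infant SD tried, 1.28, equals 5/(2 × 1.96), at which 95% of infants' means would span the 5-point width of a target range.

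| Between-infant SD | Group-level SD | Change |
|---|---|---|
| 0.5 | 4.031 to 3.536 | −12.3% |
| 1 | 4.123 to 3.640 | −11.7% |
| 1.28 | 4.198 to 3.725 | −11.3% |

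The dilution is small on these assumptions.

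**The case against.** The strongest reply is that nobody could carry out the literal rule, so it cannot be what was meant. Only the histogram paragraphs speak of pooling, and they carry no test. The SD and percentage sentences carry a test and do not speak of pooling. One value per infant per range is the unit that makes the named test workable. Student's t-test also has a paired form, so the text does not contradict the design. On this view the remaining gap is a missing word or two.

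This is a fair account of the probable intention, but it does not settle the matter. It has to override the explicit reference to all valid readings in the group, and even then the pairing is still unstated.

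Several arguments about weight do stand:

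- The SD is a secondary outcome in a pilot with no power calculation.
- With positive correlation an unpaired test is conservative, so the risk is lost precision rather than false positives.
- The correlations have no source in the documents. At ρ = 0 nothing is lost: the paired half-width is 2.093 × √(2/20) = 0.66, against 0.64 unpaired.
- Section 5.2.1 does not expect withdrawals, and section 9 allows discontinuation without giving a rate, so 16 pairs is only an illustration.
- Pairing matters most for the percentage-time comparison, because that serves the primary objective.

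Section 8.2 also gives no SD analysis for TcPO₂, although 2.1.2 lists one. That is a separate gap and does not affect this point.

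**Conclusion.** The concern holds and should be fixed before analysis. As worded, the variability rule gives one SD per target range and a test with 0 degrees of freedom. No section supplies a per-infant SD or states that the test is paired. These findings rest on the text alone.

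The size of the loss from an unpaired test depends on the assumed correlation. With 20 infants, the interval half-width would be 0.64 instead of 0.55, 0.47 or 0.36 for correlations of 0.3, 0.5 or 0.7. The mixing of within- and between-infant spread is a minor matter under the assumptions tried. The main problems are the 0 degrees of freedom and the unstated pairing.

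Confidence is high on what the text says and moderate on what was intended. The practical damage is limited because the correct analysis can still be done from the data being collected.

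**What to change.** Make two changes in 8.2:

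1. Define SpO₂ variability as the SD of valid readings within each infant in each 6-hour period. Compare the two target ranges by a paired t-test over all infants with valid data in both periods (at most 20 pairs, 19 degrees of freedom), and report the mean difference with its 95% CI.
2. Reword the percentage-time sentence in the same way: for each threshold, one percentage per infant per period, compared by a paired test.

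The histogram paragraphs can stay pooled, since they are descriptive. The cost is two sentences. No new data or procedures are needed, because one-second readings are already recorded for each infant.
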